### **7.3. Method of Treatment Assigned**

After the informed consent is signed, subjects will be assigned a subject identification number using a centralized interactive web response system (IWRS). At the Baseline Visit, a centralized schema will be applied to assign subjects who meet the inclusion and none of the exclusion criteria to receive apremilast 30 mg BID, after a 5-day titration period. In addition, half of the subjects must have moderate disease activity or below, as assessed by c-DAPSA.

During the study visits, the pharmacy or authorized study personnel at the investigational site will dispense coded IP kits in accordance with the identification number assigned by the IWRS.

### **7.4. Packaging and Labeling**

For the titration period, apremilast will be supplied by Amgen Inc. to the principal investigator as blister cards. For the remaining of the study, apremilast 30 mg tablets will be supplied in HDPE bottles with child-resistant caps.

The label(s) for IP will include Sponsor name, address and telephone number, the protocol number, IP name, dosage form and strength (where applicable), amount of IP per container, lot number, expiry date (where applicable), medication identification/kit number, dosing instructions, storage conditions, and required caution statements and/or regulatory statements as applicable. Additional information may be included on the label as applicable per local regulations.

### **7.5. Investigational Product Accountability and Disposal**

The investigator, or designee, is responsible for taking an inventory of each shipment of apremilast received, and comparing it with the accompanying apremilast shipping order/packing list.

The Investigator(s) or designee(s) will verify the accuracy of the information on the form, sign and date it, retain a copy in the study file, and record the information in the IRT.

Investigational product will be stored per the storage conditions identified on the drug label. At the study site, all IP will be stored in a locked, safe area to prevent unauthorized access.

Amgen (or designee) will review with the Investigator and relevant site personnel the process for investigational product return, disposal and/or destruction including responsibilities for the site versus Amgen (or designee).

### 7.5.1. Dosing

#### 7.5.1.1. Study Medication Dispensing and Counting

After the informed consent is signed, subjects will be assigned a subject identification number using a centralized interactive web response system (IWRS). At the Baseline Visit, a centralized schema will be applied to assign subjects who meet the inclusion and none of the exclusion criteria to receive apremilast 30 mg tablets. Study medication will be dispensed as specified in Section 5, Table of Events. The tear-off label from each blister card should be pasted into the drug accountability document in each subject's record. Subjects must be instructed to return all previously issued empty blister card(s), empty study drug bottle(s) and/or unused study medication at the time that new medication is issued. A detailed record of tablets issued and returned at each visit must be maintained in the subject's record.

During the study visits, the pharmacy or authorized study personnel at the investigational site will dispense coded IP kits in accordance with the number assigned by the IWRS.

### 7.6. Investigational Product Compliance

Study personnel will review the instructions printed on the package with the study subjects prior to dispensing the IP. Investigational product will be dispensed as noted in the Table of Events, Section 5. The subjects will be instructed to return the IP containers, including any unused medication, to the study site at each visit for tablet counts and reconciliation. Subjects will be asked whether they have taken their IP as instructed at each study visit. Any problems with IP compliance will be reviewed with the subject. If the subject misses 4 or more consecutive days of dosing, Amgen must be contacted to decide whether dosing should resume or whether the subject should be terminated from the Treatment Phase of the study, and enter into the Observational Follow-up Phase.

Gross compliance problems (eg, missing 4 or more consecutive days of dosing or taking less than 75% of the doses between study visits) should be discussed with Amgen. Compliance is defined as taking between 75% and 120% of dispensed IP.

Approved

## 8. CONCOMITANT MEDICATIONS AND PROCEDURES

All medications and therapies being taken/used by the subject up to 30 days prior to the Screening Visit (Visit 1) or at any time during the study should be recorded. Prior medications for the treatment of PsA must be recorded at any time. Other key medications and therapies, such as previous treatment for TB or relevant diseases, should be recorded.

All medications and therapies, including physical therapy, for PsA and their reasons for discontinuation, should be recorded. The stop dates for all medications and therapies prohibited in the study should be recorded. Additional instructions can be found in the CRF Completion Guidelines.

### 8.1. Permitted Concomitant Medications and Procedures

All medications (prescription and non-prescription), treatments and therapies taken by the subject from screening throughout their entire participation in the study, including those initiated prior to the start of the study, must be recorded on the subject's source document and on the appropriate page of the CRF. The dose, unit, frequency, route, indication, the date the medication was started and the date the medication was stopped (if not ongoing) must be recorded. Subjects may continue receiving standard of care therapy (eg, folic acid for those on MTX) if not explicitly prohibited as per protocol. The following concomitant medications and procedures are permitted:

- Oral glucocorticoids, (on a stable dose of prednisone  $\leq 10$  mg/day or equivalent for at least 4 weeks prior to Baseline Visit [ie, Day 1]).
- Note: The stable dose of glucocorticoids must be continued and maintained from Day 1 through the Week 24 Visit. Change in doses, increase or decrease, and/or discontinuation of glucocorticoids will not be allowed except for safety reasons or for lack of availability. After the Week 24 Visit, the dose of glucocorticoids may be adjusted as clinically required.
- MTX ( $\leq 25$  mg/week, if total treatment duration is  $\geq 6$  months and on a stable dose for at least 3 months prior to baseline).
- At Week 12, subjects will be allowed to receive IA glucocorticoids, administration of up to 2 injections of  $\leq 40$  mg triamcinolone hexacetonide or equivalent (each joint).
- NSAIDs or narcotic analgesics (must be on a stable dose for at least 4 weeks prior to the Baseline Visit [ie, Day 1]).
- Note: The stable dose of NSAIDs or narcotic analgesics must be continued and maintained from Day 1 through the Week 24 Visit. Change in doses, increase or decrease, and/or discontinuation of NSAIDs or narcotic analgesics will not be allowed except for safety reasons or for lack of availability. After the Week 24 Visit, the dose of NSAIDs or narcotic analgesics may be adjusted as clinically required.
- NSAIDs or narcotic analgesics that are administered on an as needed basis (PRN) should be recorded on the Prior/Concomitant Medications page of the CRF.
- Loperamide and antidiarrheal drugs with antisecretory effect (eg, racecadotril).

- Low dose aspirin (acetylsalicylic acid, up to 325 mg per day) for cardiovascular prophylaxis.
- Birth control medications/barrier methods for FCBP subjects.
- Low-potency topical glucocorticoids (or locally available equivalent) as background therapy for treatment of psoriasis on the face, axillae and groin in accordance with the manufacturers' suggested usage during the course of the study.
- Coal tar shampoo and/or salicylic acid scalp preparations on scalp psoriasis lesions.
- A nonmedicated skin emollient (eg, Eucerin® cream) for body psoriasis lesions only.

Medications for conditions other than PsA and psoriasis, which are not prohibited in Section 8.2, are permitted and must be recorded in the subject's source documents and as a concomitant medication on the CRF.

The following therapy will be permitted after the Week 24 Visit for subjects with worsening arthritic symptoms of PsA:

- Change of NSAID type and/or dose
- Administration of no more than 40 mg intramuscular (IM) or intra-articular (IA) glucocorticoid (triamcinolone hexacetonide or equivalent) at a single visit, up to Week 36, not to exceed two glucocorticoid IM and/or IA administrations in any 6 month-interval. Injected joints should not be counted during the visits that will take place within 4 weeks of the intra-articular injection.
- Short course ( $\leq 2$  weeks) of low-dose oral glucocorticoids (prednisone  $\leq 10$  mg/day or equivalent), to be completed up to Week 36 and not to exceed one course in a 6-month interval

In order to minimize the impact on ongoing efficacy assessments, the investigator should use the least intensive regimen to ameliorate the subject's worsening PsA symptoms. After Week 24, if subjects experience a decrease in PsA clinical disease activity, the investigator may opt to taper the background treatment; however, only one agent may be reduced or tapered at any one time. After the first agent's taper has been completed (not required to be zero), the dose must be stable for at least 4 weeks prior to starting the taper of the next agent. Subjects are recommended to have a reduction of background therapy in the following order: first MTX, second glucocorticoids and third NSAIDs or other pain medication. If clinically indicated, the investigator may opt to reduce the medications in a different order. Any further questions/concerns regarding dose reductions can be discussed with the Sponsor.

All other prohibited medications listed in Section 4.4 (Exclusion Criteria) and Section 8.2 (Prohibited Concomitant Medications and Procedures) remain in effect through the end of the subject's participation in the study.

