15. Rheumatic autoimmune disease other than PsA, including, but not limited to: systemic lupus erythematosus, mixed connective tissue disease, scleroderma, polymyositis, or fibromyalgia
16. Prior history of or current inflammatory joint disease other than PsA (eg, gout, reactive arthritis, RA, ankylosing spondylitis, Lyme disease), which confounds the ability to interpret data from the study
17. Prior treatment with any biologic DMARD
18. Prior treatment with more than 2 csDMARDs

Approved

19. Use of the following systemic therapy(ies) within 28 days of the Baseline Visit (ie, Visit 2, Day 1): cyclosporine or other calcineurin inhibitors, glucocorticoids exceeding 10 mg daily prednisone equivalent, as well as mycophenolate
20. Use of MTX within 4 weeks of the Baseline Visit (ie, Visit 2, Day 1), unless subject is on stable doses for at least 3 months and total treatment duration with MTX is  $\geq$  6 months
21. Use of LEF within 12 weeks of the Baseline Visit (ie, Visit 2, Day 1), unless subject has taken cholestyramine, 8 g three times daily  $\times$  11 days after stopping LEF
22. Previous treatment with a JAK inhibitor (including tyk2 inhibitor)
23. Prior treatment with apremilast, or participation in a clinical study involving apremilast
24. Use of intra-articular (IA) glucocorticoid injection within 8 weeks before the Baseline Visit (ie, Visit 2, Day 1).
25. Use of any investigational drug within 4 weeks of the Baseline Visit, or 5 pharmacokinetic/pharmacodynamic half-lives, if known (whichever is longer)

Approved

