## 5. TABLE OF EVENTS

Table 13: Table of Events

Visit Number	1 Screening	2 Baseline	3	4	5	6	7	Early Termination j  Assessments performed for Early Termination	Observational Follow-up  8 (or subsequent to Early Termination Visit)
	Week	Days -28 to 0	0	8 (+/-1 week)	16 (+/-1 week)	24 (+/-1 week)	36 (+/-1 week)		
Study Entry and General Assessments									
Informed Consent	X	-	-	-	-	-	-	-	-
Demographics	X	-	-	-	-	-	-	-	-
Medical History	X	-	-	-	-	-	-	-	-
Inclusion/Exclusion Criteria	X	X	-	-	-	-	-	-	-
Prior/concurrent Medications	X	X	X	X	X	X	X	X	X
Prior/concurrent Procedures	X	X	X	X	X	X	X	X	X
Biomarkers and Safety Assessments									
Vital Signs	X	X	X	X	X	X	X	X	-
Height	X	-	-	-	-	-	-	-	-

Approved

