#### **6.4.1. Magnetic Resonance Imaging (MRI)**

The MRI assessments will be conducted following the procedures outlined in the MRI manual, at scheduled visits according to Section 5 (Table of Events). The clinical and the MRI assessments should be performed on the same day, with the MRI scans always performed after the clinical visit. Exceptionally, MRI scans can be performed within 7 days after the clinical assessments. The baseline MRI must be performed within 7 days after the first administration of IP. The subsequent MRIs should be performed at Week 24 + 7 days and Week 48 + 7 days. All MRI visits should be scheduled well in advance to allow for proper planning. In addition, it is recommended to schedule 2 MRI visits (an initial and a repeat visit) for each MRI time point in order to be assured of a high-quality MRI scan at each protocol-specified time point. The initial and repeat MRI visits should be scheduled approximately 7 to 14 days apart to allow enough time for confirmation of quality scans from the initial MRI. If the initial MRI scans are of acceptable quality, then the scheduled repeat MRI session can be canceled.

All MRI technicians will receive training on specific MRI positioning and joint placement, further details of which are provided in the Study Procedures Manual. The MRI technician will ensure the quality of each MRI prior to the subject leaving the radiology facility.

The adjudication of the results, when two readers are involved, will be done through the consensus procedure between the two readers. The readers will be able to share the screen and discuss the data, then amend the final scoring. All data, the original and the consented results will be recorded and stored in the imaging database and later incorporated into the clinical database to be available for statistical analysis.

Refer to [Appendix P](#), [Appendix Q](#) and [REDACTED] for details of MRI indices.

For more detailed information on the specific procedures and the consistent acquisition of MRI images, see the MRI Manual.

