## **6.4.5. Clinical Efficacy Assessments**

### **6.4.5.1. Joint Assessments**

[figure not shown]
A modified ACR joint count that includes the distal interphalangeal joints of the fingers and toes (the “78 tender and 76 swollen” joint scores; [Appendix C](#)) will be performed at every visit. The joints to be evaluated are illustrated in [Figure 2](#). Joint tenderness and swelling will be noted as “present” or “absent,” with no quantitation of severity.

In case of digit(s) with dactylitis, each joint of the affected digit must be evaluated for tenderness and swelling.

Joints that are swollen or tender should be marked with a tick.

In the event that a joint is injected with intra-articular glucocorticoid (allowed only after Week 24 assessments are completed, and up to the Week 36 Visit), this joint should be marked by an “X” and won’t be assessed if the study visit occurs within 4 weeks (28 days) of the intra-articular (IA) injection.

In order to maintain consistency throughout the study, the same evaluator should perform the joint assessments for a given subject at a study site at each study visit.

Approved

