### **8.3. Prohibited Concomitant Medications and Procedures**

The following concomitant medications and concomitant procedures are prohibited, except as permitted in Section 8.1.

- DMARDs (conventional synthetic or biologic) for treatment of PsA, except for MTX ( $\leq 25$  mg/week) if on stable dose at least 3 months prior to Baseline Visit and with total treatment duration  $\geq 6$  months.
- Treatment with IA glucocorticoids outside the time points specified in Section 8.1, or administration of more than 2 injections of  $\leq 40$  mg triamcinolone hexacetonide or equivalent (each joint)

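### Protocol 8.1 permits intra-articular glucocorticoid at Week 12 and 6.4.5.1 forbids it until after the Week 24 assessments, so a scored joint of the scanned hand may be injected before the primary MRI

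*Protocol*

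**What the plan says.** Five parts of the protocol bear on IA glucocorticoid.

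- Section 8.1, permitted medications: "At Week 12, subjects will be allowed to receive IA glucocorticoids, administration of up to 2 injections of" at most 40 mg, followed by the words each joint in brackets. No window is given and no joint or hand is excluded.
- Section 8.1, later list: "The following therapy will be permitted after the Week 24 Visit for subjects with worsening arthritic symptoms of PsA". This list includes an IM or IA glucocorticoid dose of at most 40 mg at one visit, up to Week 36. It does not say that IA use is confined to that period.
- Section 6.4.5.1, on joint counts: IA injection is "allowed only after Week 24 assessments are completed, and up to the Week 36 Visit". An injected joint is marked and is not to be "assessed if the study visit occurs within 4 weeks (28 days) of the intra-articular (IA) injection".
- Section 8.3, prohibitions: "Treatment with IA glucocorticoids outside the time points specified in Section 8.1, or administration of more than 2 injections of" at most 40 mg each joint. The limit of two is that of the Week 12 bullet.
- Section 4.4, criterion 24, excludes "Use of intra-articular (IA) glucocorticoid injection within 8 weeks before the Baseline Visit".

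The Table of Events has visits at Weeks 8, 16, 24, 36 and 48 and none at Week 12. Doses of methotrexate, NSAIDs and oral glucocorticoids are to stay stable from Day 1 to the Week 24 Visit (Protocol 3.1). The primary endpoint is the Week 24 change in the PsAMRIS composite of bone marrow edema, synovitis and tenosynovitis. It is scored on fingers 2 to 5 of the hand with the greater burden of swollen joints or dactylitis (SAP 4.2.4.2).

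**The concern.** The plan holds systemic anti-inflammatory background fixed until the primary assessment and bars IA steroid for 8 weeks before baseline. The Week 12 bullet is the exception, and another section of the same protocol contradicts it. A site that follows 8.1 may inject a joint that a site following 6.4.5.1 may not.

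The scanned hand is chosen because it is the more inflamed one, so its finger joints are plausible targets for injection. The primary result is a single-arm mean change with a confidence interval. Protocol 1.3.2 justifies the absence of placebo on the ground that MRI inflammation would not be expected to improve without intervention. A local steroid injection into a scored joint is a second intervention. With no control arm, any effect remaining at Week 24 would be counted as an effect of apremilast.

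The conflict also reaches the per-protocol population. Protocol 9.2 excludes subjects with major deviations in the first 24 weeks, and SAP 5.2.3 excludes those with major violations that might affect the primary endpoint. Where one section permits an injection and another forbids it, its status under either definition is undetermined.

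**Working it through.** **The plan's own figure.** The plan gives no number on this point. Its sample size reproduces: (1.96 × 6.2 / 1.24)² = 96.04 evaluable, and 96.04 / 0.80 = 120.05, against 120 stated. Nothing below depends on it.

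**Which rule governs.**

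1. 6.4.5.1 contains the word only, so it leaves no room for Week 12.
2. The later list in 8.1 can be read as additional to the Week 12 bullet, because it does not claim to be exhaustive.
3. 8.3 prohibits IA use outside the 8.1 time points and repeats the Week 12 limit of two injections. It supports the Week 12 bullet.
4. 8.1 and 8.3 together therefore favour Week 12 being permitted. Neither mentions 6.4.5.1, so the contradiction remains in the current text.

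**Gap from injection to primary MRI.** The Week 24 visit may fall in Weeks 23 to 25 (Table of Events), and the scan may follow by up to 7 days ("The subsequent MRIs should be performed at Week 24 + 7 days and Week 48 + 7 days").

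- Initial scan: Week 23 to Week 26.
- Gap from Week 12: 23 − 12 = 11 weeks to 26 − 12 = 14 weeks, nominally 12.
- Repeat scans lengthen it. Protocol 6.4.1 spaces a repeat 7 to 14 days after the initial scan, so one repeat can give 14 + 2 = 16 weeks. SAP 4.2.4.1 allows up to two repeats and reads all images regardless of window.
- Comparator: the 8-week washout in criterion 24.

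**Sensitivity to the undefined date.** The 11-week minimum assumes injection at exactly Week 12.

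- Injection as late as Week 15, earliest scan at Week 23: 23 − 15 = 8 weeks, equal to the washout.
- Assumption that a site uses its next scheduled visit, Week 16 ± 1: shortest 23 − 17 = 6 weeks, longest initial-scan gap 26 − 15 = 11 weeks, nominal 24 − 16 = 8 weeks. The lower end is shorter than the washout.

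**Would the records show which joint was injected?** Week 12 is day 84. The Week 16 visit (day 112 ± 7) falls on days 105 to 119, which is 21 to 35 days after injection. The 28-day marking rule covers days 105 to 112, or 8 of the 15 possible visit days, and misses the other 7. Medications with dose, route and dates are recorded (8.1), and "Prior/concurrent Procedures" are collected at every visit (Table of Events). The readable text does not say that either record names the joint.

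**Handling in the SAP.** The readable text handles injected joints only for tender and swollen joint counts (SAP 4.2.4.9) and, by reference, the enthesitis indices. A PsAMRIS rule may exist in the Imaging Charter or in text not shown in SAP 4.2.4.4.1. It would not decide whether injection is allowed.

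**The case against.** The best reply is that the governing sections are 8.1 and 8.3, that they agree, and that 6.4.5.1 is a parenthesis inside joint-count instructions. This stands in part. A reader might infer that the protocol gives sites no way to decide. The documents do not support that, since the balance is towards Week 12 being permitted. That reading leaves the more troublesome rule in force, though: permission before the primary MRI, with the index hand not excluded.

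The second reply is that no consequence is shown. The nominal gap exceeds the washout accepted before baseline, the analysis is descriptive with no hypothesis test, and the stated purpose is preliminary evidence. This also stands as far as size goes. An 8-week eligibility rule does not prove absence of effect, but no document shows that one remains.

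A reader might also infer that two injected finger joints would affect 2 of 12 scored regions, about 17% of the endpoint. The documents do not support that. Bone marrow edema is scored at two sites per joint, the composite formula is redacted (SAP 4.2.4.3.7), and it is unclear whether the limit of two is in total or per joint.

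Finally, the per-protocol criteria are deferred by plan until before database lock. That is legitimate, and it leaves time to name this case. It does not tell sites what they may do meanwhile.

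**Conclusion.** The contradiction is certain: both statements are current protocol text, and no readable section reconciles them. On the likelier reading, a scored finger joint of the index hand may be injected before the primary Week 24 MRI, and whether that is a deviation is undetermined.

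The size of any bias is unknown and may be zero. A reader might infer that the primary mean change is shifted in favour of apremilast. The documents give neither an injection rate nor a residual steroid effect, so no shift can be claimed. What they do support is a gap of at least about 11 weeks for an injection at exactly Week 12, longer with repeat scans, against the 8-week washout. That reassurance rests on a date to which the protocol attaches no visit or window.

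The point should be fixed because the conflict concerns treatment of the joints that form the primary endpoint in a trial with no control arm, and the remedy is small.

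**What to change.** Make Protocol 6.4.5.1, 8.1 and 8.3 agree, in one of two ways.

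1. Delete the Week 12 bullet from 8.1 and align the matching limit in 8.3.
2. If Week 12 use is intended, correct 6.4.5.1, state a window around Week 12, and bar injection of finger 2–5 joints of the index hand before the Week 24 MRI.

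In either case, name any pre-MRI injection of those joints as a major deviation when the per-protocol criteria are finalised. Check that the medication, procedure or joint-assessment records identify the injected joint; a new CRF field may not be needed.

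The per-protocol exclusion is supportive only. It selects on a post-baseline event, plausibly in subjects who are doing worse, and it leaves the full-analysis-set estimate unchanged. SAP 6 says that such analyses might be conducted, while SAP 6.1 says that they will be; the SAP should settle on the latter.

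The cost is a short amendment. Because it changes permitted treatment, it needs written IRB/EC approval under Protocol 13.5. Investigators also lose some freedom to give rescue injections in the scanned hand before Week 24. The sample size does not change.
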